In the **patient-driven SMA model (all elements in Figure 1)**, patients receive a curriculum with both diabetes and mental health content. In the spirit of whole-person orientation to care, this curriculum is delivered by a multidisciplinary care team, including health educators, behavioral health providers, medical providers, and peer mentors. To support autonomy, patients in a given SMA cohort select the topics they want and need at that particular point in time (i.e., choose the topics and the order in which they are presented). To support competence, the curriculum emphasizes building skills (e.g., problem-solving, goal setting, communication skills) and enhancing self-efficacy. To support relatedness, SMAs are co-facilitated by diabetes peer mentors, and peer mentors are available to patients outside of the group visit setting for individual meetings. These needs-supportive elements may enhance self-determined motivation and help overcome known barriers to diabetes self-management behaviors; these elements are expected to enhance not only clinical outcomes, but also patient-centered outcomes, such as diabetes distress.

Table 2. Features of Comparator SMA Models

| | Standardized SMAs | Patient-Driven SMAs |
|---------------------------------|--|--|
| Same for both groups | | |
| No. of sessions | 6 (consisting of diabetes and mental health sessions) | |
| Educational components | Diabetes and mental health with goal setting and psychosocial support topics (TTIM curriculum) | |
| SMA coordinator | Scheduling and documentation | |
| Medical provider | Medication management by billable provider (Physician Assistant, Nurse Practitioner, or MD/DO); Answer patient-specific medical questions with group present | |
| Distinguishing features | | |
| Patient topic choice | Order of and time spent on TTIM topics are set for all SMA cohorts | Patients in each SMA cohort select order of and time spent on TTIM topics |
| Health educator role | Lead instructor for all educational components | Co-instructor with peer mentor for non-mental health topics |
| Behavioral health provider role | Not involved in SMAs | Co-instructor with peer mentor for mental health topics; Answer patient-specific mental/behavioral health questions with group present |
| Peer mentor role | Not involved in SMAs | Co-instructor for all group visits; 1x1 peer access |

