| Standard care team members for both SMA models | Health Educator (RN, RD, or CDE) | Group DSME/SMS instructor | Deliver TTIM self-management education |
| | Medical Provider (MD, NP, or PA) | Medical management | Prescribing provider attends during the last 20 minutes of each group to permit reimbursement. |
| | SMA Coordinator | Coordination and scheduling of TTIM sessions, care team members, and patients | Pre- and post-visit data collection by telephone Schedule patients for group visits Coordinate sessions and schedule BHP involvement (Patient-driven SMAs only) |
| Additional care team members for patient-driven SMAs | Behavioral Health Provider | Instruction and Q&A for mental health SMA topics | Co-lead instruction on mental/behavioral health topics and open-ended discussion/question and answer |
| | Diabetes Peer Mentor (CHW, lay person, patient navigator) | Co-instructor Peer mentoring | Co-lead instruction with HE/BHP (topic based) Share personal experience in group context 1x1 support outside group visit |

C.4.3.1c Aim 1c. Implement patient-driven and standardized diabetes SMAs in 20 primary care practices

In Aim 1c, 20 practices will be randomly assigned to either patient-driven or standardized SMA using covariate constrained randomization and then will implement SMAs, supported by technical assistance from the practice coach. Implementation will be overseen by [name] and managed by the implementation project manager.

Assessment of Practice Characteristics for Covariate Constrained Randomization. Prior to randomization to condition, a representative for each participating practice will complete a brief assessment to collect information that will be used in the covariate constrained randomization (CCR) procedure described below. This information will include patient and practice characteristics that are likely to influence the practice's ability to implement the intervention(s) or be associated with the outcome, such as practice size, practice type (FQHC, private practice), and patient panel characteristics, including race/ethnicity and payer mix (% Medicaid).

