Provider and staff study participants. Key organizational leadership, providers and other clinic staff will be invited to participate in practice surveys and interviews, and also participate in training and implementation.

C.4.4.2b Interventions and Comparators. The comparator interventions are:

1. Standardized diabetes SMA model, led by a HE using standardized curriculum content
2. Patient-driven diabetes SMA model, co-led by a multidisciplinary care team (HE, peer mentor, and BHP) using patient-driven curriculum content

Selection of interventions and comparators (RQ-5). As described above, patients and other stakeholders engaged in this research selected the SMA features to be tested. These features characterize the **patient-driven SMA model**, which will be compared to the **standardized SMA model**. The comparison condition (standardized SMA model) was selected as it reflects the more typical approach to SMAs in current clinical practice (a set curriculum delivered by a qualified health educator), according to practices engaged in this research. The selection of the TTIM curriculum – and the collaboration with [name], who developed and tested TTIM – was based on the topics of interest to patients engaged in BCT. *It is important to note that regardless of which SMA model a patient receives, patients will have access to all available care team members as is standard in their practice; we will assess contact with care team members outside the context of group visits and include it as a possible confounder in analysis.*

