(diabetes peer mentor). Each professional care team member is present only for the portions of the visit(s) in which they have a role; thus, HEs, BHPs, and medical providers will not overlap. As in the standardized model, the HE serves as the primary instructor, and the medical provider does medical management. Distinguishing features of patient-driven SMAs are the BHP, who serves as the co-instructor with the peer mentor for session topics pertinent to mental health, and the diabetes peer mentor, who serves as co-instructor for all visits and reinforces the curriculum by providing a personal experience perspective. The classic TTIM intervention includes “peer educators”, so that peer mentor roles are already described in the TTIM manual. BHPs help patients learn skills for coping and understanding the relationship between stress and health, explore the emotional side of diabetes, address adherence and motivation, and help patients engage in the ambivalence they feel. BHPs will deliver manualized content on TTIM content relevant to the topic of interest and be available for open discussion, an advantage being they can answer any questions specific to their area of expertise better than HEs, who do not have licensure as mental health professionals. The peer mentor will foster engagement, self-efficacy and behavioral modeling, address healthy behaviors, provide social and emotional support, suggest resources, and address questions that may arise from a “consumer” perspective. Peer mentors will be available to provide one-on-one support either in person or by telephone.

Another key feature of the patient-driven model is that patients choose the topics and the order of sessions, from the comprehensive TTIM curriculum (Appendix A). The topics are set for the first session (introductions, setting the stage) and last session (debriefing and maintenance), but are otherwise open for patient prioritization. At the first session, patients in each SMA cohort will be guided by the co-instructors to collectively choose the order of the remaining TTIM sessions, and emphasis and time spent on the topics from those TTIM sessions. Depending on the topics selected and the order of sessions, the SMA coordinator will schedule the BHP for mental health sessions.

C.4.4.2c Outcomes and Measures.

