Patient-level clinical outcomes (Aim 2a). We will gather clinical outcomes data (HbA1c, blood pressure, body mass index) from participating practices’ EHRs. All encounter data (dates, locations, visit and provider types, diagnosis codes), lab results and vital signs measures from 9 months before through 9 months after each patient’s initial SMA visit will be requested. Diagnosis codes (ICD-9/10) will be used to compute a comorbidity index⁷⁷ and to corroborate diagnosis of mental illness. Prescription data will be used to assess insulin dependence.

Patient reach and engagement in SMAs (Aim 2b). We will assess reach and engagement in terms of acceptance (i.e., what proportion of patients agree to participate in SMAs?) and participation (i.e., what proportion of SMAs do patients attend?), defined by Raue and Sirey.⁷⁸ Attendance at each session and total attendance for each of the 6 sessions, as well as any reasons for dropout, will be recorded by the SMA coordinators in a spreadsheet.

Practice-level outcomes measures (Aim 2c).

Practice quality of care, team-based care, and resource requirements. We will administer several validated practice-level measures to all practice staff and providers, as summarized in Table 5. Practice staff and providers in participating practices will be asked to complete survey measures assessing aspects of practice context (which often influence efforts to improve diabetes care⁷⁹), including measures of relational coordination (using the Relational Coordination Survey,⁸⁰ a measure of team-based care and important factor in chronic illness care in primary care teams⁸¹), practice CCM-consistent care (using the Assessment of Chronic Illness Care [ACIC])⁸², and role in SMAs. Those involved in SMAs will also complete measures of SMA resource requirements using a time-driven activity-based costing [TDABC] framework⁸³ to assess staff time use, workflows, required materials and supplies, and other resources needed to deliver each SMA model, distinguishing between early and late implementation phases. To assess practice culture, the Practice Culture Assessment will be administered to all practice staff.

Table 4. Outcomes, Measures and Data Sources

| Outcome Domain | Construct | Source | Metric/Measure | Timing | Respondent / Unit | Administered /Collected by |
|--|---------------------------------|-----------------------------------|--|--|-------------------------|--|

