| | | Survey | TDABC framework. ⁸³ | Baseline, 9, 24 months | Clinical team | Qualitative Co-I and PRA |

Quantitative data collection. Data collection procedures are as follows: **Patient participation data** will be tracked by the SMA coordinator in a spreadsheet. At each SMA session, the instructor will complete a check-in sheet noting the TTIM topics covered and any care team members and patients in attendance, and provide this information to the SMA coordinator for data entry. Most **patient surveys** will be administered to patients by the SMA coordinator (during SMA, by telephone or online, as determined in Aim 1a) prior to the first and last SMA sessions; As surveys are clinically relevant, they will be scored and made available to patients and instructors to inform discussion (and for patient-driven SMAs, topic selection) during the SMAs. **Patient cost and time surveys** will be administered separately by a PRA with the patients recruited for patient interviews, as these cannot justifiably be considered part of clinical care. The SMA coordinator will attempt to collect surveys for all patients, including those who stop attending sessions. The SMA coordinator will be responsible for survey administration, scoring and entry into a local database (e.g., a custom EHR template in the patient's record or a separate database with the patient's medical record number [MRN]³⁷). This ensures survey data can be linked at the patient level with clinical data. MRN will be replaced with a random identifier prior to transfer to the study team (IR-2).

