Practice interviews on perceptions of value and sustainability. One-on-one, in-person key informant interviews⁸⁶ will be conducted with practice members involved in SMAs at baseline, midpoint and endpoint post-implementation. Three to five key informants per practice (all care team members involved in SMAs, varies by condition) at each time period will be interviewed individually, in person by [name] (Co-I) or a PRA. Interview guides will cover practice perceptions of the value and sustainability (burden, complexity and potential for widespread uptake) of patient-driven and standardized diabetes SMAs. A semi-structured interview guide will be developed for each time period. Baseline interviews will focus on importance and interest in the upcoming SMAs, factors thought to affect adoption of the SMAs, and anticipated patient response to the SMAs. Midpoint and endpoint interviews will elicit the participant's experiences with the SMAs, including a cognitive task analysis of the intervention as delivered in the practice, to provide a detailed understanding of fidelity and any possible adaptations, while illuminating gaps in understanding.⁸⁷ Endpoint interviews will also specifically focus on recommendations for other practices and plans for continuing SMAs. This information will be considered in light of contextual factors such as practice structure and patient panel characteristics.

C.4.4.2d Analytic Plan (Methodology Standard IR-3)

The analytic plan includes both Quantitative (section C4.4.2d.1) and Qualitative (section C4.4.2d.2) components.

C4.4.2d.1 General Quantitative Approaches. For this cluster randomized trial, descriptive statistics will be computed for baseline patient and practice characteristics, initially reporting on differences between: (1) different intervention arms and (2) patient *dropouts* vs. *non-dropouts* (MD-4). Patient-level covariates will be screened in bivariate analyses and included in multivariate analysis if related to the outcome at $p < .2$, are associated with dropout, or used in the

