randomization procedure.⁸⁸ **Covariates (to adjust for potential confounding) and potential moderators will include the following:** mode of delivery of SMA (in-person vs. telehealth), age, gender, race/ethnicity, comorbidity index, insulin dependence, baseline diabetes distress, health literacy, and mental illness. Recent literature on cluster randomized trials notes that imbalance in covariates is more of a problem than for individually randomized trials, and covariates should be included to improve precision and should be selected prior to analysis.^{55,88,89} In the event normality assumptions are not met, we will use transformations to normalize distributions, ordinal or Poisson regression where appropriate, and/or the appropriate link function (e.g. logit link for dichotomized measures).⁹⁰⁻⁹² We will employ intent to treat analyses using general (generalized) linear mixed models (GLMMs) to incorporate data structures that are both hierarchical and longitudinal.^{91,93-97} Hypothesis tests will be two-sided with $\alpha = .05$ or p values reported. Goodness of fit statistics and model fitting diagnostics will be used to assess for influential points, outliers, overdispersion and heteroscedasticity and to evaluate alternative model specifications.⁹⁰ All statistical analyses will be performed using SAS version 9.4 (SAS Institute Inc., Cary, N.C.).

Missing Data (MD-2). Prior to beginning analyses described below to address study hypotheses, we will examine the data carefully to determine whether patterns of missing are ignorable (MCAR or MAR) or non-ignorable (MNAR).⁹⁸⁻¹⁰¹ If so, we will employ likelihood-based methods that utilize all available data (MD-4), adjusting for covariates that are associated with missingness (MD-3). If missingness is non-ignorable we will employ pattern mixture models.¹⁰² Sensitivity analyses will be carried out using multiple imputation approaches (MD-5).

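### Out-of-group care-team contact is called a possible confounder with no limit by role or timing, so post-randomisation contact, including assigned peer support, could enter the effect models (minor)

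*Combined protocol and SAP*

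**What the plan says.** **The rule.** Section C.4.4.2b (Interventions and Comparators) notes that patients in both arms keep their practice's usual access to care team members. It continues: "we will assess contact with care team members outside the context of group visits and include it as a possible confounder in analysis". No role, time window or exclusion is given.

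**Peer contact as intervention.** Section C.2.1 says "peer mentors are available to patients outside of the group visit setting for individual meetings", and gives this as part of how the patient-driven model supports relatedness. Table 2 lists one-on-one peer access among the features that distinguish the arms; peer mentors have no part in the standardized SMAs. Table 3 names the peer mentor as an additional care team member of the patient-driven arm, with the duty "1x1 support outside group visit". The description of the patient-driven SMAs in C.4.4.2b adds: "Peer mentors will be available to provide one-on-one support either in person or by telephone".

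**Covariates.** Section C4.4.2d.1 says "Patient-level covariates will be screened in bivariate analyses and included in multivariate analysis if related to the outcome" at p < .2. Association with dropout or use in the randomisation also qualifies a variable. The screen is not restricted to baseline variables. The named list is "mode of delivery of SMA (in-person vs. telehealth), age, gender, race/ethnicity, comorbidity index, insulin dependence, baseline diabetes distress, health literacy, and mental illness"; contact is not on it. The same section commits to intent-to-treat analysis.

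**Sources of contact data.** Section C.4.4.2c requests "All encounter data (dates, locations, visit and provider types, diagnosis codes), lab results and vital signs measures from 9 months before" to 9 months after the first SMA visit. Appendix B, worksheet item 6d, tracks connections to the care team.

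**The concern.** A confounder adjustment is meant for something that differs between arms for reasons other than the intervention. Contact after the first SMA occurs after randomisation and may be changed by the arm. For the peer mentor it is more than that: it is something one arm is assigned and the other is not. Adjusting for it would estimate the effect of the patient-driven model with part of the model held fixed, which is not the intent-to-treat contrast.

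At stake is the consistency of secondary results. A sensitivity analysis could disagree with the primary analysis only because it removed part of the effect. An engagement comparison could be adjusted for something that follows from engagement. Because C.4.4.2b says to include contact and the C4.4.2d.1 list leaves it out, the choice could also be made after the data are seen.

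**Working it through.** The plan gives no figure to reproduce on this point. The check has four steps. Every input on contact is assumed, because the documents give none.

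**1. Does the rule reach peer contact?** Table 3 makes the peer mentor a care team member and places the one-on-one support outside the group visit. C.4.4.2b covers contact with care team members outside group visits. Read literally, the second includes the first. Nothing elsewhere restricts the rule to usual-care contact or to contact before the first SMA.

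**2. Primary model (Quantitative analysis plan, Hypothesis I).** There are two time points, and the effect is the arm-by-time term. A contact total C for each patient, entered as a main effect, adds the same amount δC at both times. With complete data the arm-by-time term is the between-arm difference in mean within-patient change, and δC cancels in Y₁ − Y₀. In simulation (20 practices of 46 patients; variances 0.03 practice, 0.47 patient, 0.50 residual) the shift was 0.0000 with complete data. With 18% random loss the mean absolute shift was 0.0004.

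**3. Change-score sensitivity analysis.** Here the arm coefficient itself is tested, so nothing cancels. Take the true effect as 0.30, the hypothesised size in C.4.1, with a share s running through peer contact. Let usual contact be Poisson with mean u in both arms, and peer contact Poisson with mean p in the patient-driven arm only. Adjust for total contact:

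- effect per peer contact: b = 0.30·s/p
- pooled within-arm slope on total contact: b·p/(2u + p)
- between-arm difference in mean contact: p
- adjusted arm effect: 0.30·[1 − s·p/(2u + p)]

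| u, p | s = 10% | s = 25% | s = 50% |
|---|---|---|---|
| 2, 1 | 0.294 | 0.285 | 0.270 |
| 1, 1 | 0.290 | 0.275 | 0.250 |
| 1, 2 | 0.285 | 0.263 | 0.225 |
| 1, 3 | 0.282 | 0.255 | 0.210 |

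For example, with u = 1, p = 3, s = 25%: 0.30·[1 − 0.25·3/5] = 0.255. Simulation with 18% missing data agrees to within about 0.005. At 10–25% mediation the estimate is about 0.26–0.29. Adjusting for peer contact alone is the limiting case, 0.30·(1 − s): 0.27, 0.225 or 0.15.

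**4. Hypothesis III, sessions attended.** This model reuses the covariates described earlier in the plan and tests the arm coefficient. Suppose peer contacts accrue at rate r per session attended. Let v be the within-arm variance of sessions and m the patient-driven mean. The adjusted difference is d − r²·v·m/(2u + r·m + r²·v). Assume means of 3.76 and 4.19, so d = 0.43, and v = 2.1, the value those means imply for 1–6 sessions scored from a truncated normal:

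- r = 0.1: 0.39 (u = 1) or 0.41 (u = 2)
- r = 0.25: 0.26 or 0.32
- r = 0.5: about −0.05 or 0.10
- contact unrelated to attendance within arm: 0.43, unchanged

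This shows that the model can be exposed. With no documented contact rate, it does not estimate by how much.

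**The case against.** **Context.** The rule follows directly on a clause about access that is standard in each practice, whichever model the patient receives. Peer one-on-one support is not that. A reader might infer that the plan intends to adjust for its own intervention. The documents do not support this: the natural target is usual-care contact, and the word possible softens the commitment. This stands, but it does not close the gap. The operative words are not limited to usual care, and usual-care contact after the first SMA is itself post-randomisation.

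**The named list omits contact**, and C4.4.2d.1 says covariates should be selected before analysis. The covariates reused for Hypothesis III most naturally mean that list. This also stands, so the claim is that the sections conflict, not that contact will certainly enter.

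**Peer contacts may never be recorded.** EHR encounters may not capture telephone support from a lay mentor. Table 4 shows no contact row, but it contains a blank one, so little rests on that. This stands as an uncertainty.

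**The primary result is safe.** A reader might infer bias or lost power in the primary analysis. Step 2 shows otherwise for a contact main effect. A time-varying contact term or a contact-by-time term would be different, but the plan states neither.

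**Sign and size are not established.** A reader might infer that adjustment always shrinks the effect. If contact follows distress that the baseline score misses, with nothing mediated, an assumed within-arm correlation of 0.30 and arm raising contact by 1 SD, the 0.30 becomes 0.47. If contact follows the measured score, it stays at 0.30; that route is plausible because of the surveys the plan says "they will be scored and made available to patients and instructors". A different assumed unmeasured driver, with 25% mediated, gave 0.10. These figures are illustrations only.

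**Conclusion.** The point holds as a minor inconsistency with a specific remedy. As worded, the rule in C.4.4.2b covers post-randomisation contact, including an assigned component of one arm. It therefore sits badly with the intent-to-treat commitment, and it does not agree with the covariate list.

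The primary arm-by-time estimate is essentially unaffected. Two analyses are exposed, and only if the rule is followed literally and the contact is recorded: the baseline-adjusted change-score analysis and the Hypothesis III sessions-attended model.

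For the change score, under assumed 10–25% mediation and adjustment for total contact, 0.30 becomes about 0.26–0.29. The plan's effective sample size of 193 per arm implies a standard error near √(2/193) = 0.10, so that shift is under half a standard error. For Hypothesis III the result runs from no change to loss of the whole difference, depending entirely on an assumed contact rate. The actual size in either analysis is unknown.

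**What to change.** 1. In C.4.4.2b and C4.4.2d.1, state that contact after the first SMA, including all one-on-one peer mentor contact, is not a covariate in the intent-to-treat effect models and is not eligible for the p < .2 screen.
2. Limit any confounder adjustment for contact to encounters in the 9 months before the first SMA, and make the covariate list agree with that.
3. Report contact after the first SMA by arm, with peer contact separate from usual-care contact, either descriptively or in a labelled exploratory analysis. Give its source and timing in Table 4.

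The cost is a few sentences and one table row. The pre-SMA encounters are already in the requested extract. The downside is that the main models will not adjust for concurrent usual-care contact, such as behavioral health visits in the standardized arm. Pre-SMA counts measure something different from that. Concurrent contact can still be examined in the labelled exploratory analysis.
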